6.1 PRIMARY EFFICACY ANALYSIS

6.1.1 Phase I and Phase II: Change in IRLSS total score from baseline to Day 42

The actual value of IRLSS total score on baseline and Day 42, and change from baseline to Day 42 will be summarized via descriptive statistics by treatment group for each treatment phase.

A subject data listing of IRLSS total score for each visit will be provided.

6.1.2 Phase I and Phase II: Percentage of subjects who are much or very much improved at Day 42 as measured by the CGI-I

The number (percentage) of subjects who are rated as much or very much improved with the CGI-I on Day 42 will be summarized by treatment group (for Phase I only) for each treatment phase. The denominator should be the Phase I Safety population for each treatment group in Phase I. For Phase II, the denominator is the Safety population in Phase II.

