8.5 Statistical Analyses of Efficacy

Categorical variables will be summarized with the number and percent of subjects in each treatment group with the characteristic. Quantitative variables will be summarized with the mean, median, standard deviation, minimum value, and maximum value. Baseline will be defined as the last value obtained before randomization.

Phase I

The treatment differences for the changing IRLSS score from Baseline to Day 42 will be assessed with the analysis of covariance with treatment as a fixed effect and baseline value as a covariate.

The treatment difference for the percentage of subjects who are much or very much improved at Day 42 as measured by the CGI-I will be assessed with the chi-square test.

Change from Baseline for IRLSS at Day 28, MOS at Day 42, and brain iron distribution at Day 42 will be assessed with the same method as IRLSS at Day 42. The percentage of subjects who are much or very much improved at Day 42 as measured by the PGI-I will be assessed with the chi-square test.

Phase II and III

All analyses will be descriptive.

For Phase II, the proportion of treatment **Non-Responders** in Phase I who respond to FCM in Phase II will be estimated and the IRLSS, CGI-I, PGI-I and brain iron distribution will be summarized at Day 42.

The Kaplan-Meier method will be used to estimate time from first dose of FCM to treatment intervention. Subjects in Phase III who discontinue the study before requiring treatment intervention will be censored on the day of the last contact with the Investigator.

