1.2 STUDY ENDPOINTS

1.2.1 Primary Efficacy Endpoint(s)

Primary efficacy endpoint in **Treatment Phase I** is to determine the effectiveness of FCM in improving RLS severity associated with IDA. Effectiveness will be evaluated by:

- IRLSS score change from baseline to Day 42 with comparison between FCM vs. Placebo.
- CGI-I at Day 42.

Primary efficacy endpoint in **Treatment Phase II** is to determine the effectiveness of an additional unblinded single FCM treatment in improving RLS severity in non-responders from Treatment Phase I. Effectiveness will be evaluated by:

- IRLSS score change from baseline (For Phase II the “baseline” is established on Day 42 of Phase I) compared to Day 42 of Treatment Phase II
- CGI-I at Day 42 in Treatment Phase II.

Primary efficacy endpoint in **Long-Term Extension Phase III** is to evaluate the duration of effect of FCM as defined as the number of weeks from the initial treatment without need for further treatment. Initial treatment is defined as Day 0 of Phase I for Responders in Phase I and Day 0 of Phase II for Responders in Phase II.

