1.3.3 Sample Size and Statistical Power Considerations

Enrollment was planned for 70 randomized subjects (35 per treatment group in Phase I). Based on Study 1VIT05009 in patients without IDA, approximately 50% of patients in the FCM group and 15% of patients in the placebo group are anticipated to have much or very much improvement on the CGI-I. The proposed sample size provides >85% power to detect this difference with the chi-square test. The mean treatment difference (and standard deviation) for change from baseline to Day 42 for IRLSS is anticipated to be 5.0 (7.3). The proposed sample size provides >80% power to detect this difference with a two-sided t-test with alpha=0.05.

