2. STATISTICAL METHODS

2.1 GENERAL CONSIDERATIONS

Analysis datasets will be produced according to CDISC standards. All study-collected data will be summarized in tables or graphs. Listing will be produced when appropriate and all ICH-required listings will be produced. In general, continuous variables will be summarized by number of subjects, mean, standard deviation (SD), median, minimum, and maximum values. Categorical variables will be summarized by number and percentage of subjects in each category.

In general, summary tables will present data by treatment group (for Phase I) and treatment phase.

Baseline definitions:

- Phase I: baseline (other than iron index) is the last non-missing value prior to receiving randomized study medication.
- Phase II: phase II baseline (other than iron index) is the last non-missing value prior to receiving unblinded FCM in Phase II.
- Phase I and Phase II: baseline for iron index measured by MRI is measured in screening.
- Phase III: phase III baseline is defined as Day 0 of Phase I for responders in Phase I and Day 0 of Phase II for responders in Phase II.

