6. EFFICACY ANALYSES

All efficacy analyses will be based on the Safety Population for each phase accordingly.

Statistical testing for treatment effect:

- Phase I, II and III: no formal statistical testing will be performed. Data will be reported via descriptive statistics only.

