9. SUMMARY OF MAJOR CHANGES IN THE PLANNED ANALYSES

Compared with the study protocol 1VIT15042 (Date: 4 September 2019), below items are the major changes made in this SAP:

1. Due to early termination of the study, no statistical analysis will be performed. Hence no primary, and secondary end points will not be tested with statistical model.
2. Physical examinations was removed from safety analysis list and any significant findings will go to medical history or adverse event summaries.
3. The secondary endpoint “Number of Subjects who remained in the study to Week 52” will be summarized in disposition table for n (%) of study completer. It will not be considered as an efficacy endpoint in this SAP.
4. Adverse events of special interest were added in this SAP in Section 7.1.1.

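### The SAP keeps a comparative Phase I primary endpoint but plans no FCM-minus-placebo difference, confidence interval or baseline adjustment for IRLSS or CGI-I, while a secondary responder endpoint keeps a p-value

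*SAP*

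**What the plan says.** The supplied protocol makes two Phase I endpoints co-primary (Protocol 8.4.1): IRLSS change to Day 42, FCM against placebo, and the percentage much or very much improved on CGI-I. Under Protocol 8.5 the IRLSS treatment difference "will be assessed with the analysis of covariance with treatment as a fixed effect and baseline value as a covariate"; CGI-I gets a chi-square test. Phases II and III were already descriptive there, so the SAP's cutback falls on the randomised phase.

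The SAP keeps the comparative endpoint. Section 1.2.1 lists "IRLSS score change from baseline to Day 42 with comparison between FCM vs. Placebo". The analysis sections do not deliver it:

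- SAP 6, for all three phases: "no formal statistical testing will be performed. Data will be reported via descriptive statistics only".
- SAP 6.1.1, for IRLSS total score: "change from baseline to Day 42 will be summarized via descriptive statistics by treatment group for each treatment phase".
- SAP 6.1.2, for CGI-I: number and percentage improved in each arm, over that arm's Phase I Safety population.
- SAP 2.1, on what a descriptive summary contains: "continuous variables will be summarized by number of subjects, mean, standard deviation (SD), median, minimum, and maximum values".
- SAP 9, item 1, on why: "Due to early termination of the study, no statistical analysis will be performed". It adds that primary and secondary endpoints will not be tested with a model.

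One between-arm analysis survives. SAP 6.2.6 says Phase I differences in responder percentage will be assessed by chi-square, with p-values shown.

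**The concern.** An endpoint defined as a comparison needs an analysis that makes the comparison. As written, the Phase I IRLSS and CGI-I results will be two columns of summaries. The natural reading is to subtract one mean from the other by eye, with no stated uncertainty for the difference and no allowance for chance baseline imbalance between small arms. The report itself would not say whether the data are compatible with the planned 5.0 points, with no effect, or with an effect in the wrong direction.

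The stated reason covers less than was removed. A trial stopped short of its sample size has lost the power its tests were designed for, so dropping confirmatory tests is reasonable. A difference with an interval can be computed at any sample size, and the interval is what shows how little a truncated trial can say.

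The surviving p-value makes this worse. The one between-arm result would be a bare p-value on a secondary endpoint, while the primary endpoints get no contrast.

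**Working it through.** **Inputs from SAP 1.3.3.** 35 per arm; IRLSS difference 5.0 with SD of change 7.3; two-sided alpha 0.05 (written for the t-test, assumed for the chi-square); CGI-I 50% against 15%. The number randomised at termination is not given, so a range is shown.

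**The plan's own figures.** IRLSS power at 35 per arm is 0.806 (noncentral t, 68 df) or 0.817 (normal approximation), against a stated >80%. CGI-I power is 0.896 (uncorrected chi-square approximation), against a stated >85%. Both reproduce.

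**Width of the missing IRLSS interval, unadjusted.** Half-width = t(0.975, 2n−2) × 7.3 × √(2/n), where n is the number per arm with both values.

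| n per arm | t | √(2/n) | half-width (points) | interval if the observed difference is 5.0 |
|---|---|---|---|---|
| 35 | 1.995 | 0.239 | 3.48 | 1.52 to 8.48 |
| 20 | 2.024 | 0.316 | 4.67 | 0.33 to 9.67 |
| 15 | 2.048 | 0.365 | 5.46 | −0.46 to 10.46 |
| 10 | 2.101 | 0.447 | 6.86 | −1.86 to 11.86 |
| 5 | 2.306 | 0.632 | 10.65 | −5.65 to 15.65 |

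At 15 per arm or fewer the half-width exceeds the planned effect.

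**Width of the missing CGI-I interval.** Wald half-width at the planned rates = 1.96 × √[(0.5×0.5 + 0.15×0.85)/n]: 20 percentage points at 35 per arm, 27 at 20, 31 at 15, 38 at 10 and 54 at 5, around a planned difference of 35. This shows scale only; a Newcombe interval is preferable at small n.

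**What baseline adjustment would add.** The documents give neither a baseline SD nor a slope. Assume a baseline SD of 5 and a slope of change on baseline of 0.5 in size.

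- Variance of change: 7.3² = 53.29. Part explained by baseline: 0.5² × 5² = 6.25. Remainder: 47.04. Ratio: 47.04/53.29 = 0.88, a cut of about 12%.
- Half-width at 15 per arm: t(0.975, 27) × √47.04 × √(2/15) = 2.052 × 6.859 × 0.365 = 5.14, against 5.46 unadjusted.
- SD of the chance baseline gap at 15 per arm: 5 × √(2/15) = 1.83. Amount passing into the raw difference in change: 0.5 × 1.83 = 0.9 point for a one-SD gap.

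So adjustment brings a modest gain in precision and removes a shift of roughly a point in an unlucky draw.

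**What can be rebuilt from the planned output.** SAP 6.1.1 gives baseline, Day 42 and change for each arm, and SAP 2.1 gives n, mean and SD for each. The unadjusted difference and its t-interval follow directly. For the adjusted one, the within-arm covariance of baseline and Day 42 is (Var baseline + Var Day 42 − Var change)/2, which fixes the ANCOVA slope, difference and standard error. This needs the same subjects at both visits and is limited by rounding; otherwise the IRLSS listing in 6.1.1 serves. For CGI-I, the count and denominator per arm give the risk difference and its interval.

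**Internal consistency.** SAP 6 excludes formal testing in every phase and SAP 9 excludes it for primary and secondary endpoints, yet 6.2.6 specifies a test with p-values. These cannot all stand.

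**The case against.** The strongest defence is that nothing is concealed and little is lost. SAP 6 and SAP 9 state the move to descriptive reporting and give early termination as the reason. Protocol 8.5 names ANCOVA and a chi-square test but never specifies a confidence interval, so intervals go beyond what was promised. A competent reader can rebuild the estimates from the tables. At 5 per arm the interval would span more than 20 points and say almost nothing. All of this stands. It limits how serious the point is, but it does not explain why a comparative endpoint should have no comparative output.

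Four stronger readings are tempting, and the documents do not support them:

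- **All randomised comparison has been removed.** It has not: 6.2.6 keeps one, on responder status, which is itself built from IRLSS and CGI-I. The gap concerns the two primary endpoints.
- **This is an undisclosed deviation.** SAP 9 discloses it. That section measures changes against a protocol dated 4 September 2019, whereas the supplied protocol carries April 2016 dates. The ANCOVA wording is therefore from the supplied version, but SAP 9 itself presents dropping model-based tests as a change.
- **The effect can no longer be estimated.** It can, as shown above. What is missing is a planned and reported estimate.
- **ANCOVA would sharpen the result greatly.** The familiar (1+ρ)/2 variance ratio gives 65–85% for ρ of 0.3–0.7, but it assumes equal baseline and Day 42 variances. With a baseline SD of 5 and a change SD of 7.3, equal variances would require ρ = 1 − 53.29/50 = −0.07. The entry floor of IRLSS 15 or more also makes equal variances doubtful. About 88% is the figure consistent with the assumptions used here.

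**Conclusion.** The point holds as a gap in planned reporting. The SAP states a comparative Phase I endpoint, plans no effect estimate with its uncertainty for IRLSS or CGI-I, and contradicts its own no-testing rule in 6.2.6. The reason given supports dropping tests only.

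The uncertainty left unreported is large: an unadjusted IRLSS half-width of 3.5 points at 35 per arm, 4.7 at 20, 5.5 at 15 and 6.9 at 10, against a planned effect of 5.0. These widths rest on the plan's SD of 7.3 and on assumed sample sizes. The benefit of adjustment (variance down about 12%, and about 0.9 point of imbalance removed for a one-SD gap at 15 per arm) rests on an assumed baseline SD of 5 and slope of 0.5. Because the change is disclosed and the estimates are largely recoverable, this is an inexpensive improvement to make before reporting, not a flaw that invalidates the trial.

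**What to change.** 1. **SAP 6.1.1:** add the FCM-minus-placebo difference in IRLSS change at Day 42 from the Protocol 8.5 ANCOVA (treatment plus baseline), with a 95% CI and no p-value.
2. **SAP 6.1.2:** add the Phase I difference in percentage much or very much improved, with a 95% CI, for example Newcombe's.
3. **Both:** analyse by randomised arm and label as estimation only. SAP 6 currently bases efficacy on the Safety population, which SAP 2.2.2 groups by treatment actually received, although SAP 2.2.1 defines an ITT set.
4. **SAP 6.2.6:** replace the chi-square p-value with the responder difference and a 95% CI, which brings it into line with SAP 6 and SAP 9.
5. **SAP 9, item 1:** state that tests, not estimates, were dropped because of early termination. This is true only once step 4 is done.

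The cost is SAP wording and a few lines of output, with no new data. The downside is that wide intervals become visible, and at very small n they may be nearly uninformative.

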1.2.2 Secondary Efficacy Endpoint(s)

Treatment Phase I and Phase II:

- Change in IRLSS score from Baseline to Day 42. (Treatment Phase I and II)
- IRLSS score change from Baseline (For Phase II the “Baseline” is established on Day 42 of Phase I) compared to Day 42 of Treatment Phase II.
- CGI-I and PGI-I at each visit and percentage of subjects who are much or very much improved at Day 42. (Treatment Phase I and II)
- Change in sleep quality (MOS Sleep) from Baseline to Day 42. (Treatment Phase I and II)
- Estimate the proportion of treatment non-responders in Phase I who respond to FCM in Phase II for each randomized treatment group. (Phase II only)
- Change in substantia nigra iron index from Baseline to Day 42. The index will be determined using measures of MRI relaxation rate (R2*) or Quantitative Susceptibility Mapping (QSM). (Treatment Phase I and II)
- Change in iron index (R2* or QSM) for thalamus and motor cortex from Baseline to Day 42. (Treatment Phase I and II).

Treatment Phase III:

- Change in IRLSS total score from baseline to each scheduled visit.
- Number (and percentage) of subjects who remain in the study to Week 52.

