6.2 SECONDARY EFFICACY ANALYSES

6.2.1 Phase I and II: Change in IRLSS total score from baseline to Day 42 (Non-responders in Phase I Placebo group)

The change is defined as IRLSS total score at Day 42 minus IRLSS total score at baseline in each phase. The number of subjects, mean, median, standard deviation, minimum (min) and maximum (max) for the observed values, and change from baseline will be reported in summary table.

6.2.2 Phase I and II: Change in IRLSS total score from baseline to Day 42 (Non-responders in Phase I FCM group)

IRLSS total score from baseline to Day 42 between Phase I and Phase II will be summarized. The change is defined as IRLSS total score at Day 42 minus IRLSS total score at baseline in each phase. The number of subjects, mean, median, standard deviation, minimum (min) and maximum (max) for the observed values, and change from baseline will be reported in summary table.

6.2.3 Phase I and Phase II: CGI-I and PGI-I score at Day 42

The number (percentage) of subjects of each category will be summarized for CGI-I and PGI-I, separately.

6.2.4 Phase I and Phase II: Percentage of subjects who are much or very much improved at Day 42 as measured by the PGI-I

The number (percentage) of subjects who are rated as much or very much improved with the PGI-I on Day 42 will be summarized by treatment group (for Phase I only) for each treatment phase.

6.2.5 Phase I and Phase II: Change in sleep quality measured by MOS from baseline to Day 42

The actual value of MOS score on baseline and Day 42, and change from baseline to Day 42 will be summarized via descriptive statistics by treatment group (for Phase I only) for each treatment phase.

6.2.6 Phase I and Phase II: Number (percentage) of treatment non-responders at Day 42 of Phase I who respond to FCM in Phase II

The number (percentage) of treatment non-responders at Day 42 in Phase I who are turned into responders in Phase II, and the treatment responders of each phase, will be summarized by treatment group, separately. For Phase I, treatment differences in percentage will be assessed with the chi-square test, p-values will be presented. The subjects who missing responder/non-responder classification will be considered as non-responder.

6.2.7 Phase I and Phase II: Number (percentage) of treatment responders at Day 42

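### The Phase II primary CGI-I percentage, and the Phase II PGI-I and MOS results, are pooled over the Phase I arms, which mixes first-course and repeat-course FCM; the SAP separates these groups for other Phase II outcomes

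*SAP*

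**What the plan says.** SAP 1.2.1 names two Phase II primary measures: IRLSS change from the Phase II baseline, and CGI-I at Day 42 of Phase II.

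- **CGI-I (SAP 6.1.2).** The improved percentage "will be summarized by treatment group (for Phase I only) for each treatment phase". The section adds: "For Phase II, the denominator is the Safety population in Phase II". Protocol 8.2 defines that population as all Phase I Non-Responders who receive FCM in Phase II, whichever arm they came from.
- **PGI-I (6.2.4) and MOS (6.2.5).** Both carry the same limit of the treatment split to Phase I. SAP 6.2.3, which tabulates the CGI-I and PGI-I categories, states no grouping.
- **IRLSS.** SAP 6.1.1 says that the scores "will be summarized via descriptive statistics by treatment group for each treatment phase", without saying what the treatment group is in Phase II. SAP 6.2.1 and 6.2.2 then plan separate summaries for Phase I placebo and Phase I FCM Non-Responders.
- **Responder status.** SAP 1.2.2 lists as a secondary endpoint: "Estimate the proportion of treatment non-responders in Phase I who respond to FCM in Phase II for each randomized treatment group". SAP 6.2.6 and 6.2.7 carry this out by treatment group, and 6.2.7 specifies the Phase I group.

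SAP 6 makes all efficacy reporting descriptive. SAP 9 records that the study ended early.

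**The concern.** Everyone in Phase II receives open-label FCM, but the two source groups are in different situations. A former placebo subject is having a first course. A former FCM subject is having a second course after a first that did not produce a response. Whether a first open-label course helps and whether repeating a failed course helps are separate questions.

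A single percentage over both groups is a weighted average, and its weights are set by Phase I outcomes and by who passes the ferritin and TSAT criteria for Phase II. Only one arm received IV iron in Phase I, so those criteria may remove more former FCM subjects than former placebo subjects. The printed figure could then change with no change in the benefit of either course.

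PGI-I has a further difficulty. Its form (Protocol Appendix I) asks about change since the start of the study, so by Day 42 of Phase II it covers two FCM courses for one group and placebo followed by one FCM course for the other.

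At stake is the interpretation of a primary summary. No test, error rate or power calculation is affected.

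**Working it through.** **The plan's own figures.** The plan gives no figure for Phase II. Its Phase I planning figures (SAP 1.3.3) reproduce and are not in dispute. With 35 per arm, 50% versus 15% and two-sided alpha 0.05 (stated for the t-test, assumed here for the chi-square test):

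- Pooled proportion = (0.50 + 0.15)/2 = 0.325.
- SE under no difference = √(2 × 0.325 × 0.675/35) = 0.1120.
- SE under the alternative = √((0.25 + 0.1275)/35) = 0.1039.
- z = (0.35 − 1.96 × 0.1120)/0.1039 ≈ 1.26, so power is 89.6%. Exact enumeration of the uncorrected chi-square test gives 90.3%. The plan states more than 85%.
- For IRLSS, 5.0/7.3 × √(35/2) = 2.87 on 68 degrees of freedom gives 80.6%. The plan states more than 80%.

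**Inputs for the Phase II illustration**

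- From SAP 1.3.3: 35 per arm; improved on CGI-I, 50% with FCM and 15% with placebo.
- Assumed: all 70 complete Phase I; CGI-I non-improvement stands in for Non-Responder status; every former placebo Non-Responder enters Phase II; a first FCM course in Phase II improves 50%.
- Assumed and varied: the repeat-course rate r, and the share of former FCM Non-Responders who pass the laboratory criteria.

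**Step 1: who is available for Phase II**

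- Former placebo: 35 × (1 − 0.15) = 29.75.
- Former FCM: 35 × (1 − 0.50) = 17.5.
- Total 47.25, of which 29.75/47.25 = 63% are former placebo.

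**Step 2: the pooled percentage if all pass the laboratory criteria**

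Pooled = (29.75 × 0.50 + 17.5 × r)/47.25

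- r = 0: 14.875/47.25 = 31.5%
- r = 15%: 17.5/47.25 = 37.0%
- r = 30%: 20.125/47.25 = 42.6%
- r = 50%: 23.625/47.25 = 50.0%

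**Step 3: the same rates with a different arm mix**

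If half of the former FCM Non-Responders pass, 8.75 enter. At r = 15% the pooled figure is (14.875 + 8.75 × 0.15)/38.5 = 42.0%, against 37.0% in Step 2.

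| Former FCM passing | Former placebo share | r = 0 | r = 15% | r = 25% | r = 50% |
|---|---|---|---|---|---|
| 100% | 63.0% | 31.5% | 37.0% | 40.7% | 50.0% |
| 75% | 69.4% | 34.7% | 39.3% | 42.3% | 50.0% |
| 50% | 77.3% | 38.6% | 42.0% | 44.3% | 50.0% |
| 25% | 87.2% | 43.6% | 45.5% | 46.8% | 50.0% |

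Reading down a column, the benefit of each course is fixed and only the mix changes. A table split by Phase I arm would show 50% and r separately in every row.

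**The case against.** The strongest reply is that the plan as a whole already addresses both questions. Phase II IRLSS is separated by Phase I arm in SAP 6.2.1 and 6.2.2, and responder status in 6.2.6 and 6.2.7. CGI-I improvement is one component of the responder definition. Protocol 8.4.1 and 8.5 ask for Phase II CGI-I without an arm split, and SAP 2.1 shows treatment group for Phase I as its general table rule. The study ended early, so planned counts may not describe the data.

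Most of this stands, and it rules out three stronger readings.

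- **That the two Phase II primary measures are demonstrably on different footings.** A reader might infer this by setting 6.1.1 against 6.1.2. But 6.1.1 does not define the Phase II grouping. SAP 2.2.2 summarises the Safety population by treatment actually received, which in Phase II is FCM for everyone. If 6.1.1 already split by Phase I arm, 6.2.1 and 6.2.2 would largely repeat it. Both primaries may be pooled.
- **That the per-arm endpoint in SAP 1.2.2 is unmet.** That endpoint concerns responder status, and 6.2.6 and 6.2.7 deliver it.
- **That the SAP departs from the protocol.** No protocol text requires a CGI-I split in Phase II.

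The reply does not remove the point itself. A Responder has an IRLSS of 10 or less, or a higher score with CGI-I improvement and no request for more treatment. The CGI-I percentage by arm cannot be recovered from that composite, and PGI-I and MOS are not part of it. With no formal testing, the summary tables are the efficacy result, so their layout matters.

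**Conclusion.** The point holds as an inconsistency within the SAP and as a primary summary that is hard to interpret. As written, the Phase II CGI-I percentage, PGI-I and MOS average first-course and repeat-course FCM, although the SAP separates these groups for Phase II IRLSS and responder status.

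On size, the range of 31.5% to 50% is an illustration. It rests on planned enrolment, full Phase I completion, all Non-Responders passing the laboratory criteria, a 50% first-course rate and an assumed repeat-course rate of 0% to 50%. It also uses CGI-I non-improvement in place of the real Non-Responder definition, which could move the counts either way. If the two courses worked equally well, pooling would not distort the percentage. The figures show how the pooled percentage behaves and do not predict this study's result.

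**What to change.** - In SAP 6.1.2, 6.2.4 and 6.2.5, show Phase II results by Phase I randomised arm, with n/N for each arm, plus an overall column.
- In 6.1.2, replace the Phase II denominator sentence so that the denominator is the Phase II Safety population within each Phase I randomised arm, and overall. Deleting the words that limit the split to Phase I would not be enough: the pooled denominator would remain, and treatment group could still be read as a single FCM group.
- In 6.1.1 and 6.2.3, state that the Phase II grouping is the Phase I randomised arm.

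The data are already collected, so the cost is a few extra columns. Cell counts will be small, more so after early termination, which is a reason to print n/N beside every percentage.

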1. INTRODUCTION

The purpose of this statistical analysis plan (SAP) is to describe the procedures and the statistical methods that will be used to analyze and report results for Protocol 1VIT15042 (Date: 4 September 2019). This SAP should be read in conjunction with the study protocol and case report forms (CRFs).

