2.2.2 Safety Population

Safety population includes all the subjects who were randomized and received at least one dose of study medication.

Summaries for safety population will be based on the actual treatment they received.

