2.4 HANDLING OF MISSING DATA

Missing data will not be imputed for descriptive statistical summaries in safety or efficacy analyses.

For the PGI-I score, missing data at Day 42 will be considered as failure in analysis.

Dates missing the day or both day and month of the year will adhere to the following conventions to classify TEAE and to classify prior/concomitant medications.

- A medication with a completely missing start date will be considered a prior medication. A medication with a completely missing stop date will be considered a concomitant medication.
- If complete AE onset date is missing and AE end date is on or after the first dose date then it will be counted as a treatment emergent AE (TEAE) for the study. If complete AE onset date is missing and AE end date is before the first dose date then it will be counted as a not treatment emergent AE (TEAE) for the study.
- If an AE or a medication has a partial missing start or stop date, the following rules will be used for imputation:
 - If year is present but month and day are missing, impute start date as January 1 of that year or first dose date if the year is the same as the year of first dose date and impute stop date as December 31 of that year.
 - If year and day are present but month is missing, impute start month as January or the month of the first dose date if the year and day is the same as the year and day of first dose date and impute stop month as December.
 - If year and month are present but day is missing, impute start date as first day of that month or first dose date if the year and month are the same as the year and month of first dose date and impute stop date as last day of that month.

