The number (percentage) of treatment responders at Day 42 of Phase I and Phase II will be summarized by treatment group in Phase I, separately. The subjects who missing responder/non-responder classification will be considered as non-responder.

6.2.8 Phase I and Phase II: Change in substantia nigra iron index from baseline to Day 42

The actual value of substantia nigra iron index on baseline and Day 42, and change from baseline to Day 42 will be summarized via descriptive statistics by treatment group (for Phase I only) for each treatment phase.

Substantia nigra iron index will be measured using MRI relaxation rate (R2*) or QSM.

6.2.9 Phase I and Phase II: Change in thalamus and motor cortex iron index from baseline to Day 42

The actual value of thalamus and motor cortex iron index on baseline and Day 42, and change from baseline to Day 42 will be summarized via descriptive statistics by treatment group (for Phase I only) for each treatment phase, separately.

Iron index will be measured using MRI relaxation rate (R2*) or QSM.

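### The SAP acknowledges early termination, but its Day 42 CGI-I, PGI-I and responder rates would count a visit lost to the stop as a treatment failure

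*SAP*

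**What the plan says.** The SAP mentions early termination once, in section 9, and draws one consequence from it: "Due to early termination of the study, no statistical analysis will be performed".

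The Day 42 response rates are built as follows.

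- Analysis set (SAP 6): "All efficacy analyses will be based on the Safety Population for each phase accordingly". Membership needs only randomization and one dose (SAP 2.2.2): "Safety population includes all the subjects who were randomized and received at least one dose of study medication". No Day 42 value is required.
- CGI-I (SAP 6.1.2): "The denominator should be the Phase I Safety population for each treatment group in Phase I". Phase II likewise uses its whole Safety Population.
- PGI-I (SAP 2.4): "For the PGI-I score, missing data at Day 42 will be considered as failure in analysis".
- Responder status (SAP 6.2.6 and 6.2.7): "The subjects who missing responder/non-responder classification will be considered as non-responder".

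Three other provisions bear on this. SAP 2.4 opens with a general statement that descriptive summaries use no imputation, and it names only PGI-I as an exception. SAP 2.3 restricts tables to scheduled visits. SAP 6.2.6 keeps a Phase I chi-square p-value for responder status, although section 6 says that no phase will be formally tested.

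**The concern.** Counting a missing outcome as failure is a defensible convention when a subject drops out, because dropping out may itself reflect lack of benefit. A visit that did not happen because the sponsor closed the study carries no such information. The SAP applies one rule to both cases, so any visit lost to the stop would mix the closing date into the efficacy percentages.

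This matters more than usual here. With model-based testing withdrawn, these percentages are a main efficacy output, and the CGI-I percentage is one of the two Phase I primary measures. The other, IRLSS change, is summarized on observed values, so the two could describe different subjects in the same arm. The responder rule also feeds the one efficacy p-value that the SAP retains.

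The supplied protocol would have worked differently. Its Phase I full analysis set (protocol 8.2) requires a post-randomization CGI-I, which the schedule places only at Day 42, so a subject without one would have left the denominator. SAP section 9 does not list this change. However, the SAP cites a protocol dated 4 September 2019 and the supplied one carries April 2016 dates, so the later text cannot be checked.

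**Working it through.** **Inputs.** Planning rates p of 50% (FCM) and 15% (placebo), with 35 subjects per arm, come from SAP 1.3.3. Two-sided alpha of 0.05 is stated there for the t-test and is assumed here for the chi-square test. The share m of an arm's Safety Population with no Day 42 value is not in the documents; 5% to 40% is assumed. The planning rates are taken as the rates among subjects who do have a Day 42 value.

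**Step 1: reproduce the plan's figure.** Power ≈ Φ{[|p1 − p2|√n − 1.96√(2p̄(1 − p̄))] / √(p1(1 − p1) + p2(1 − p2))}. With p̄ = 0.325 and n = 35:

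- (0.35 × 5.916 − 1.96 × 0.6624) / 0.6144 = 1.257, so power is 89.6%.
- Exact enumeration of the chi-square test gives 90.3% uncorrected and 85.2% with continuity correction.

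The stated bound of more than 85% holds, and the planning rates are usable inputs.

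**Step 2: trace a treated subject with no Day 42 value.** One dose puts the subject in the Safety Population. On PGI-I the subject is an explicit failure, and on responder status an explicit non-responder. On CGI-I the subject is in the denominator and cannot be in the numerator. None of these rules depends on why the value is missing.

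**Step 3: equal m in both arms.** Reported rate = p × (1 − m); gap = 0.35 × (1 − m).

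| m | FCM | Placebo | Gap (points) |
|---|---|---|---|
| 0% | 50.0% | 15.0% | 35.0 |
| 5% | 47.5% | 14.25% | 33.25 |
| 10% | 45.0% | 13.5% | 31.5 |
| 20% | 40.0% | 12.0% | 28.0 |
| 30% | 35.0% | 10.5% | 24.5 |
| 40% | 30.0% | 9.0% | 21.0 |

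The rate ratio stays at 0.50 / 0.15 = 3.33 throughout.

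**Step 4: unequal m.**

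- 20% FCM, 0% placebo: 0.50 × 0.80 − 0.15 × 1.00 = 0.25, a gap of 25 points.
- 0% FCM, 20% placebo: 0.50 × 1.00 − 0.15 × 0.80 = 0.38, a gap of 38 points.

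**Step 5: what a second rate would show.** Split m into a (lost to termination) and d (missing for other reasons). The SAP rate is p(1 − a − d). Removing only the termination-lost subjects gives p(1 − a − d) / (1 − a). With d = 0 this returns p. With a = 20% and d = 10% in both arms:

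- SAP rates: 0.50 × 0.70 = 35.0% and 0.15 × 0.70 = 10.5%.
- Second rates: 35.0 / 0.80 = 43.75% and 10.5 / 0.80 = 13.125%.

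Other missing values still count as failures in the second rate.

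**Step 6: the retained p-value.** The documents give no planning rates for responder status, so the CGI-I rates stand in as an illustration. Using the Step 1 formula at m = 20%, power is 77.3% with all 35 per arm counted (40% vs 12%), and 81.6% with the 28 observed per arm (50% vs 15%). Most of the fall from 89.6% comes from losing the data; the counting rule takes about 4 points more.

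**The case against.** The strongest reply is that no harm has been shown. The documents do not say when or how the study closed, or whether any treated subject missed Day 42 because of it. If enrolment closed and treated subjects finished a 42-day phase, m from this cause is zero and nothing changes. This stands: the effect is conditional and its size is unknown.

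Second, an all-treated denominator is a conventional conservative choice, and under 1:1 randomization a calendar stop should affect the arms about equally in expectation. That is a fair reason to keep the all-treated rate, but not to show it alone.

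Third, part of the information will be available anyway. SAP 3.1 tabulates reasons for premature discontinuation, and SAP 6.2.3 tabulates each CGI-I and PGI-I category. That helps, but neither section links the reason for a missing Day 42 value to the response rate. Protocol 4.4 asks for final procedures at withdrawal, but with SAP 2.3 limited to scheduled visits it is unclear whether those could stand in for Day 42.

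A reader might also infer more than the documents support:

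- **That the SAP was written because of the stop.** SAP 1 says only that it is to "describe the procedures and the statistical methods that will be used to analyze and report results for Protocol 1VIT15042". Section 9 links early termination to the dropped testing and to nothing else.
- **That missing CGI-I is declared a failure.** It is not. Failure follows from the denominator, and the no-imputation sentence in SAP 2.4 points the other way.
- **That the rule always narrows the treatment gap.** With unequal loss it can widen it.
- **That Week 52 retention has the same fault.** It does not. That count "will be summarized in disposition table for n (%) of study completer" and is no longer an efficacy endpoint. A subject who did not reach Week 52 is not a completer, whatever the reason, and no missing-as-failure rule applies.

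**Conclusion.** The point holds as a conditional gap in the SAP, not as a demonstrated bias. The document knows that the study ended early, yet its CGI-I, PGI-I and responder rules cannot tell a visit lost to the stop from any other missing value. If such visits exist, each affected arm's rate can only fall, by the factor (1 − m). The difference between arms falls in proportion when m is equal, and can move either way when it is not.

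The figures rest on three assumptions: the planning rates apply to subjects with a Day 42 value; m lies in the range shown; and termination-lost subjects would have responded like the others in their arm. The last is plausible for a calendar stop but cannot be tested from the documents. If m is zero, the reported rates stand unchanged.

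**What to change.** In SAP 2.4, 6.1.2, 6.2.4, 6.2.6 and 6.2.7:

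1. Report, by arm and phase, the number of treated subjects with no Day 42 value, split into 'study terminated before Day 42' and other reasons.
2. Beside the all-treated missing-as-failure rate, show the rate with only the termination-lost subjects removed from the denominator. Other missing values stay failures.
3. State the CGI-I rule for a missing Day 42 rating explicitly, so that SAP 2.4 and 6.1.2 agree.

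Showing both rates avoids having to decide which is the headline. If nobody was cut off, the first row reads zero and the question is closed. The cost is SAP wording, one flag derived from disposition dates, a few more table rows and a smaller denominator in the second rate.
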